5 STUDY ACTIVITIES

5.1 Eligibility Criteria

Subjects must meet all of the following criteria in order to be included in the study. Anything other than a positive response to the questions below will result in exclusion from study participation.

Consent

- ✔ 1. Subjects or their legally authorized representative must voluntarily **sign and date an informed consent**, approved by an IEC/IRB, prior to the initiation of any screening or study-specific procedures, and are eligible to participate per applicable local regulations.
- ✔ 2. Employees of the sponsor and/or study sites and their family members may not be enrolled in this study.
- ✔ 3. Subjects are willing and able to comply with procedures required in this protocol.

Demographic and Laboratory Assessments

- ✓ 4. Adult **individuals**, at least 18 years old (subjects must also meet the legal age of majority per local law).
- ✓ 5. **Laboratory values** meeting the following criteria within the screening period prior to the first dose of study drug:
 - Serum AST $\leq 2 \times$ ULN;
 - Serum ALT $\leq 2 \times$ ULN;
 - Serum total bilirubin $\leq 2 \times$ ULN, except for subjects with isolated elevation of indirect bilirubin relating to Gilbert syndrome;
 - Total WBC count $> 3,000/\mu\text{L}$;
 - ANC $> 1,500/\mu\text{L}$;
 - Platelet count $> 100,000/\mu\text{L}$;
 - Hemoglobin $> 10 \text{ g/dL}$ (100 g/L).

Disease/Condition Activity

- ✓ 6. Subject has **moderate to severe genital psoriasis** (Study-G) defined as sPGA-G ≥ 3 or **moderate to severe scalp psoriasis** (Study-S) defined as PSSI ≥ 12 , scalp IGA ≥ 3 , and $\geq 30\%$ of the scalp affected at Screening and Baseline.
- ✓ 7. Subject has BSA $\geq 1\%$ at Screening and Baseline. At least 60% of subjects within Study-G and within Study-S will each comprise subjects with Baseline BSA $\geq 10\%$.
- ✓ 8. Subject has an **overall sPGA** ≥ 3 ("moderate" or "severe") at Screening and Baseline.
- ✓ 9. Subject has inadequate control and/or intolerance to topical treatment, phototherapy and/or systemic therapy for the treatment of psoriasis affecting the genitalia (Study G) or scalp (Study-S).
- ✓ 10. Subject must be a candidate for systemic therapy or phototherapy as assessed by the investigator.
- ✓ 11. Subject has a clinical diagnosis of chronic plaque psoriasis with or without psoriatic arthritis for at least **6 months** before the Baseline Visit.

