 - History of an **organ transplant** that requires continued immunosuppression.
 - **Active or suspected malignancy** or history of **any malignancy** within the last 5 years except for successfully treated non-melanoma skin cancer or localized carcinoma in situ of the cervix.
 - **Non-plaque forms of psoriasis** (including guttate, erythrodermic, or pustular) or current drug-induced psoriasis (including an exacerbation of psoriasis from beta blockers, calcium channel blockers, or lithium).
 - **Active skin disease**, other than psoriasis, that could interfere with the assessment of psoriasis.

Contraception

- ✓ 20. For all females of child-bearing potential; a **negative serum pregnancy test** at the Screening Visit and a **negative urine pregnancy test** at Baseline prior to the first dose of study drug.

- ✓ 21. Female subjects of childbearing potential must practice at least 1 protocol-specified **method of birth control**, that is effective from Study Day 1 through at least 140 days (20 weeks or as guided by the local risankizumab label [if approved], whichever is longer) after the last dose of study drug (local practices may require 2 methods of birth control). Female subjects of non-childbearing potential do not need to use birth control.
- ✓ 22. Female subjects may not be **pregnant, breastfeeding, or considering becoming pregnant** during the study or for approximately 140 days (20 weeks or as guided by the local risankizumab label [if approved], whichever is longer) after the last dose of study drug.

Concomitant Medications

- ✓ 23. Subject must not have had **previous exposure to IL-23 inhibitors** including but not limited to guselkumab, tildrakizumab, ustekinumab, mirikizumab, or risankizumab.
- ✓ 24. Subject must not have received **any live viral or bacterial vaccine** (with the exception of replication deficient viral vaccines, [e.g., JYNNEOS®, Imvamune®, or Imvanex®] for the prevention of monkeypox disease) within 4 weeks prior to the first dose of study drug or expect the need for live vaccination during study participation including at least 140 days (20 weeks or as guided by the local risankizumab label [if approved], whichever is longer) after the last dose of study drug.
- ✓ 25. Subject must not have been treated with **any investigational drug** within 30 days or 5 half-lives of the drug (whichever is longer) prior to the first dose of study drug or be currently enrolled in another interventional clinical study.

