Subjects will be withdrawn from the CTE if any of the following occur in addition to what is stated in Section 5.5:

- A subject no longer derives benefit from risankizumab per investigator assessment.
- Subject has reasonable access to commercial risankizumab in the country of participation per investigator and/or sponsor assessment.
- Subject receives a live vaccine (with exception of non-replicating live vaccines).

Drug Assignment

Subjects will have the option to receive continued treatment with open-label risankizumab in CTE if they completed the study (Week 52) and continue to tolerate and derive benefit from risankizumab treatment, but do not have risankizumab commercially available and/or do not have reasonable access to risankizumab.

Safety Considerations

If any urine pregnancy test is positive, a serum pregnancy test will be performed locally. If the serum pregnancy test is positive, study drug must be permanently discontinued. If the serum pregnancy test is borderline, it should be repeated ≥ 3 days later. If the repeat serum pregnancy test is:

- Positive, the study drug must be permanently discontinued;
- Negative, the subject can continue in the study;
- Still borderline ≥ 3 days later, this will be considered documentation of continued lack of a positive result and the subject can continue in the study (unless prohibited locally) in the absence of clinical suspicion of pregnancy and other pathological causes of borderline results.

A pregnant or breastfeeding female will not be eligible for continuation or be allowed to continue study drug.

Independent Data Monitoring Committee, Cardiovascular Adjudication Committee, Anaphylaxis Adjudication Committee

Not applicable for CTE data.

Statistical Analysis for Safety

Safety analysis for the CTE may be conducted separately as needed.

Refer to [Appendix E](#) for additional information.

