- g. Serum pregnancy test is conducted at Screening and at other visits only if urine pregnancy test is positive. Negative serum pregnancy test results must be confirmed prior to study drug dosing.
- h. Only performed in case of a suspected anaphylactic reaction. Refer to anaphylaxis testing Section 9.1 below.

Urinalysis

Dipstick urinalysis will be completed by the central laboratory at all required visits. Specified abnormal macroscopic urinalyses defined as leukocytes, nitrite, protein, ketones, or blood greater than negative, or glucose greater than normal will be followed up with a microscopic analysis at the central laboratory.

Pregnancy Tests (Serum and Urine)

Pregnancy testing should not be performed for postmenopausal women. Determination of postmenopausal status will be made during the Screening Period based on the subject's history and confirmed by FSH, if appropriate.

A pregnant or breastfeeding female will not be eligible for participation or continuation in this study.

Pregnant subjects must discontinue from study drug treatment. Refer to Section 5.5 of the protocol for additional details.

Serum Pregnancy Test

A serum pregnancy test will be performed for all female subjects of childbearing potential (defined in the protocol) at Screening. The serum pregnancy test will be sent to and performed by the central laboratory. If the serum pregnancy test is positive, the subject is considered a screen failure. If the serum pregnancy test is borderline, study drug should be held and the test should be repeated ≥ 3 days later to determine eligibility.

If the repeat serum pregnancy test is:

- Positive, the subject is considered a screen failure;
- Negative, the subject can be enrolled into the trial;
- Still borderline ≥ 3 days later: If no clinical suspicion of pregnancy and there are other pathological causes of borderline results, the borderline results will be considered documentation of continued lack of a positive result and the subject can be enrolled into the study.

Urine Pregnancy Test

A urine pregnancy test will be performed for all females of childbearing potential at the Baseline Visit prior to the first dose of study drug. Additional urine pregnancy tests for female subjects of childbearing

potential will be performed at visits indicated in Section 2.1. More frequent pregnancy tests will be performed throughout the study if required per local/country requirements.

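### Criterion 20 and a manual footnote require a negative serum pregnancy test, but the Operations Manual conditionally enrols a subject whose serum test is borderline twice, and the extension words that condition differently

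*Protocol*

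**What the plan says.** **Eligibility (Protocol Section 5.1).** Criterion 20 reads: "For all females of child-bearing potential; a negative serum pregnancy test at the Screening Visit". It also asks for a negative urine test at Baseline before the first dose. The section opens with a strict rule: "Anything other than a positive response to the questions below will result in exclusion from study participation". Criterion 20 has no borderline category and does not point to the Operations Manual.

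**Operations Manual Section 3.12 (Protocol Appendix G), laboratory table.** Footnote f asks for a urine test at each dosing visit, with a negative result confirmed before dosing. Footnote g places the serum test at Screening, and at other visits only after a positive urine test. It adds: "Negative serum pregnancy test results must be confirmed prior to study drug dosing".

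**Operations Manual Section 3.12, Serum Pregnancy Test.** "If the serum pregnancy test is borderline, study drug should be held and the test should be repeated ≥ 3 days later to determine eligibility". The repeat test has three outcomes: positive (screen failure), negative (may be enrolled) and still borderline. For the last: "If no clinical suspicion of pregnancy and there are other pathological causes of borderline results", then "the borderline results will be considered documentation of continued lack of a positive result and the subject can be enrolled into the study".

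**Extension (Protocol Section 12, Safety Considerations).** After a positive urine test, a serum test is done locally. If it is borderline and still borderline on repeat at least 3 days later, the subject may continue, unless local rules forbid it, "in the absence of clinical suspicion of pregnancy and other pathological causes of borderline results".

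**The concern.** The result that keeps a subject out under the eligibility criteria and footnote g lets her in under the serum-test paragraph. Appendix B binds investigators to both the protocol and the operations manual, and Section 5.9 does not allow intentional deviations except to remove an immediate hazard. The text available states no order of precedence. A site that follows the serum-test paragraph therefore enrols a subject who fails criterion 20, and SAP Section 7.3 counts eligibility violations as protocol deviations.

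The extension adds a second, separate problem. It uses almost the same borderline rule, but its wording on pathological causes can be read in the opposite sense.

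At stake is a patient-safety check, the pregnancy test that precedes study drug. No efficacy result depends on it.

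**Working it through.** The documents give no figure to reproduce, and no arithmetic applies. The check sets the texts side by side for a subject of childbearing potential.

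**Step 1. Does a twice-borderline result count as negative?** No. The manual lists negative and still borderline as separate outcomes, and describes the second as a continued lack of a positive result. Criterion 20 asks for a "negative serum pregnancy test". A subject who is negative on repeat raises no dispute; one who is still borderline has no negative serum result on record.

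**Step 2. Main study, two borderline serum results at least 3 days apart.**

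| Subject | Criterion 20 with the Section 5.1 exclusion rule | Footnote g | Serum Pregnancy Test text | Agreement? |
|---|---|---|---|---|
| No clinical suspicion, other pathological cause present | Excluded | No dosing | May be enrolled | **No** |
| No clinical suspicion, no other pathological cause | Excluded | No dosing | No permission given | Yes |
| Clinical suspicion | Excluded | No dosing | No permission given | Yes |

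The conflict is confined to the first row. Footnote g and the serum-test text sit in the same manual section, so the manual also disagrees with itself there.

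**Step 3. Can the manual be read as qualifying criterion 20?** Where Section 5.1 intends an exception or a pointer, it writes one. Criterion 5 carves out Gilbert syndrome within the criterion, and criterion 18 sends latent tuberculosis to Operations Manual Section 3.12. Criterion 20 does neither.

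**Step 4. Extension, serum test borderline twice, no clinical suspicion.** The phrase in Section 12 has two readings. Taken literally, both the suspicion and the other causes must be absent. Taken as loose drafting of the manual's condition, suspicion must be absent and another cause present.

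| Other pathological cause | Serum text, Section 3.12 (enrolment) | Section 12, literal (continuation) | Section 12, as loose drafting (continuation) |
|---|---|---|---|
| Present | May be enrolled | No permission given | May continue |
| Absent | No permission given | May continue | No permission given |

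On the literal reading the cause condition is reversed; on the loose reading the two texts match. The documents do not say which is meant.

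**Step 5. Section 12 against the footnotes.** Section 12 reaches the serum test only through a positive urine test. Footnote f requires a negative urine result before dosing at every dosing visit. Operations Manual Section 2.3 schedules urine tests and dosing at each extension visit and refers to Section 3 for details, and stopping risankizumab ends extension participation. Continuing therefore means further dosing in practice, and the texts do not explain how that fits a positive urine test that was never followed by a negative serum result.

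**The case against.** The strongest reply is that this is a minor wording gap with safeguards around it. Much of that stands, and it rules out several stronger readings that a reader might infer.

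- *Every twice-borderline subject gets opposite instructions.* Not supported. The manual sets two conditions, and where either fails it agrees with criterion 20 and footnote g.
- *The exclusion of pregnant women contradicts itself.* Not supported. Criterion 22, Protocol Section 6.1, Section 12 and Operations Manual Section 3.12 all bar or discontinue pregnant subjects. The conflict is over which serum result satisfies the testing criterion.
- *A woman could be dosed with no negative pregnancy test, exposing a fetus to both Period A doses.* Not supported as it stands. Criterion 20 requires a negative urine test at Baseline, footnote f requires one before each dose, a positive urine test stops dosing, and criterion 21 requires contraception. Half of the subjects in Period A receive placebo. Exposure at both doses would need an unsuspected pregnancy, two non-positive serum tests and negative urine tests at both Baseline and Week 4.
- *The extension plainly gives the opposite rule.* Not established. Section 12 is ambiguous and governs a different decision: continuing a treated subject on a local serum test after a positive urine test, not enrolling her on a central-laboratory screening test. It does not cause the criterion 20 conflict.

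The urine safeguard does not settle the eligibility conflict, because criterion 20 asks for a negative serum test and a negative urine test. Nor does it answer the extension point, where the rule begins with a positive urine test.

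**Conclusion.** The inconsistency is real and narrow. For a subject with two borderline serum tests at least 3 days apart, no clinical suspicion of pregnancy and another pathological cause, criterion 20 and footnote g exclude her and the serum-test paragraph admits her. Following the manual then produces an eligibility deviation.

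The documents do not say how many subjects this could concern; it is likely to be few and may be none. The negative urine test before dosing limits the exposure risk. Sample size, power, type I error and the estimands are unaffected, and the ITT populations include everyone randomized whatever the deviation.

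The extension wording is a second, separate defect. The reversal of the pathological-cause condition depends on a literal reading of an ambiguous phrase, but the ambiguity itself and the lack of fit with footnote f are on the page. The point is worth acting on because it concerns a safety check and is cheap to correct. This review takes no position on which rule is right.

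**What to change.** Reconcile five places so that they state one consistent rule and refer to one another: criterion 20 in Protocol Section 5.1; footnotes f and g of the laboratory table in Operations Manual Section 3.12; the Serum Pregnancy Test paragraph in that section; and the Safety Considerations text in Protocol Section 12. The wording should make clear what a repeated borderline serum result means for eligibility and for dosing. It should say without ambiguity how another pathological cause bears on the decision, and how the extension rule fits the negative urine result that footnote f requires. What the rule says is for the sponsor's clinicians to decide.

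The cost is a few sentences in the protocol and Operations Manual. No analysis, sample size or SAP text has to change.

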3.13 Subject Withdrawal

All attempts must be made to determine the primary reason for discontinuation of study drug or study participation. The information will be recorded on the appropriate eCRF page. However, these procedures should not interfere with the initiation of any new treatments or therapeutic modalities that the investigator feels are necessary to treat the subject's condition. Following discontinuation of study drug, the subject will be treated in accordance with the investigator's best clinical judgment, irrespective of whether the subject decides to continue participation in the study.

4 SAFETY MANUAL

4.1 Methods and Timing of Safety Assessment

[figure not shown]
All serious and nonserious adverse events which could be related to study procedures, (e.g., infection at liver biopsy site, done during screening) will be collected from the time the subject signed the study-specific informed consent until study drug administration. From the time of study drug administration until the follow-up phone call (20 weeks [140 days] after the last dose of study drug), all nonserious and SAEs will be collected whether solicited or spontaneously reported by the subject.

The completion of the study for a subject is defined as one following:

- The date of the completed follow-up call (20 weeks after the last dose), as applicable
- The date of the Week 52 visit (for subjects who enter the optional CTE)

- The date of the last study visit (for subjects who prematurely discontinue and do not consent to and/or complete the follow-up call)
- The date of commercial risankizumab initiation (for subjects who initiate commercial risankizumab)

After the treatment-emergent AE window of 20 weeks (140 days) following the last dose of study drug, only spontaneously reported SAEs will be collected (nonserious AEs will not be collected).

4.2 Recording Data and Analyses of Safety Findings

An AE can result from use of the drug as stipulated in the protocol, as well as from accidental or intentional overdose, drug abuse, or drug withdrawal. Any worsening of a pre-existing condition or illness is considered an AE. Worsening in severity of a reported AE should be reported as a new AE. Laboratory abnormalities and changes in vital signs are considered to be AEs only if they result in discontinuation from the study, necessitate therapeutic medical intervention, meet criteria as specified in the protocol and/or they are clinically significant and the investigator considers them to be AEs (as outlined in relevant sections).

Adverse events will be coded using the MedDRA. The number and percentage of subjects with TEAEs (i.e., any event that begins or worsens in severity after initiation of study drug through 20 weeks (140 days) after the last dose of study drug) will be tabulated by primary MedDRA SOC and preferred term. The tabulation of the number of subjects with treatment-emergent AEs by severity grade and relationship to study drug also will be provided. Subjects reporting more than 1 AE for a given MedDRA preferred term will be counted only once for that term using the most severe grade for the severity grade table and the most related for the relationship to study drug tables. Subjects reporting more than 1 type of event within an SOC will be counted only once for that SOC.

4.3 Reporting Adverse Events and Intercurrent Illnesses

In the event of an SAE, whether associated with study drug or not, the investigator will notify Clinical Pharmacovigilance within 24 hours of the site being made aware of the SAE by entering the SAE data into the EDC system. SAEs that occur prior to the site having access to the EDC system, or the EDC

system is not operable, should be documented on the SAE nonCRF forms and emailed (preferred route) or faxed to Clinical Pharmacovigilance within 24 hours of the site being made aware of the SAE.

Email: [contact]

[contact]

For safety questions, contact the Immunology Safety Team at:

Immunology Safety Team

Email: [contact]

For any subject safety concerns, please contact the physician listed below:

Primary Therapeutic Area Medical Director

EMERGENCY MEDICAL CONTACT:

[REDACTED], MD PhD

AbbVie

[name]

[name]

Contact Information:

Office:

Mobile:

Fax:

Email:

In emergency situations involving study subjects when the primary Therapeutic Area Medical Director is not available by phone, please contact the 24-hour AbbVie Medical Escalation Hotline where your call will be re-directed to a designated backup AbbVie Therapeutic Area Medical Director:

[contact]

The sponsor will be responsible for SUSAR reporting for the IMP in accordance with Directive 2001/20/EC.

COVID-19 Pandemic-Related Acceptable Protocol Modifications

Supplemental study case report forms should be completed in the event of COVID -19 related missed/virtual visits, study drug interruptions or discontinuations, or adverse events (including capture of specific signs/symptoms of infection and testing results).

SARS-CoV-2 infections should be captured as adverse events. If the event meets the criteria for a SAE, then follow the SAE reporting directions per the protocol and above. The following COVID-19 related supplemental eCRFs should be completed (for both serious and nonserious events):

- COVID -19 Supplemental Signs/ Symptoms
- COVID-19 Status Form

Reactions known to be associated with the SARS-CoV-2 vaccine should be reported as adverse events. If the event meets the criteria for an SAE, then follow the SAE reporting directions. All adverse events associated with the SARS-CoV-2 vaccine will be linked to the vaccine on the COVID-19 Vaccine eCRF.

